### DOSE DE-ESCALATION AND RE-ESCALATION

The investigator may choose to decrease the patient's dose to the prior dose (e.g., 20 mg to 10 mg, or 10 mg to 5 mg), if clinically indicated. Dose de-escalation may occur more than once, but the minimum dose permitted is 5 mg. Reasons for dose de-escalation should be discussed with the Medical Monitor prior to changing the dose and must be documented. After dose de-escalation, patients must return for an unscheduled office visit within 4 weeks ( $\pm$  3 days) to perform the assessments detailed in Section [9.7](#).

If a patient's dose has been reduced, dose re-escalation back to a higher dose is permitted to meet the dosing objective. However, patients who dose re-escalate must have a telephone call 1 week after dose re-escalation and an unscheduled office visit 2 weeks ( $\pm$  3 days) after dose re-escalation to perform assessments detailed in Section [9.7](#).

## INTERRUPTION OF STUDY DRUG

In addition to dose de-escalation and re-escalation, the study drug administration can be interrupted, if clinically indicated. The term interruption generally refers to a temporary halt of study drug administration. All efforts should be made to resume study drug at any point during the treatment period following interruption, upon consultation with the Medical Monitor. If there are any questions regarding study drug interruption, please consult the Medical Monitor.

## RESUMING STUDY DRUG

Any patient who interrupts study drug for 14 consecutive days or more must have approval from the Medical Monitor prior to resuming study drug.

When a patient resumes study drug, after an extended interruption (e.g., more than 14 days), the site should discuss the appropriate starting dose and visit frequency with the Medical Monitor. The duration of the interruption and the reason for interruption should be taken into consideration when determining how to safely resume study drug. Following an extended interruption, when the investigator deems it is safe for the patient to return to the site for an in-person visit, the investigator should conduct an evaluation to determine whether the patient is still eligible to receive study drug and to determine the appropriate dose, in consultation with the Medical Monitor. This should include a confirmation that the patient's circumstances have not changed in a manner that would prohibit administration of the study drug (e.g., the patient is now taking an excluded medication). Once the investigator determines study drug administration is appropriate, dosing may proceed.

Patients must have a telephone call 1 week after resuming and an unscheduled office visit 2 weeks ( $\pm$  3 days) after resuming study drug to perform assessments detailed in Section 9.7.

For additional guidance on resuming drug following a positive COVID-19 test, see Section 9.11.5

### **9.11.1. Dose Escalation Period – Missed In-Person Visits**

The first 8 weeks of the trial require intense safety monitoring of patients as they progress through the dose-escalation period of the study. When in-person visits are not be feasible, due to COVID-19 or any other reason, patients who are in the dose escalation period of the study should remain on their current study drug dose. The dose at the last in-person visit, if not the goal dose, will be considered the maximum dose until completion of dose-escalation can be safely resumed (See Section 9.11.5).

Protocol specified in-clinic follow-up visits, for safety/tolerability, must be completed where possible. Required assessments for patients who are unable to have an in-person visit are described in Appendix 2.

### **9.11.2. Week 8 – 12 Visits – Missed In-Person Visits**

Patients in the maintenance period of the trial who have completed dose escalation and who have not reached the Week 12 time point must be assessed at Week 12 by conducting an in-person visit, per protocol. Patients who are unable to return to the clinic/site for a scheduled Week 12 follow-up visit should remain on their current study drug dose and have remote assessments

completed to evaluate assess safety/tolerability. These remote assessments may be conducted as described in Appendix 2.

### **9.11.3. Post-Week 12 Visits – Missed In-Person Visits**

Patients who have completed dose escalation and who have completed the Week 12 Visit must be assessed at their next scheduled visits (as outlined in Table 4). Patients who will be unable to return to the clinic/site for scheduled follow-up visits should remain on their current study drug dose and complete remote assessments to evaluate safety/tolerability until in-clinic visits can be resumed (see Section 9.11.5). These remote assessments may be conducted as described in Appendix 2.

If no in-clinic visit can be completed and remote assessments/laboratory samples cannot be collected within a reasonable time, based on the investigator's discretion, the investigator should consider whether de-escalation may be appropriate.

### **9.11.4. Dose De-Escalation and Interruption for Missed Safety and Laboratory Assessments**

From Protocol Version 7.0 forward, this text was removed, and language was placed within Section 9.11.

### **9.11.5. Resuming Study Drug After COVID-19 Interruption**

Patients who interrupt study drug due to a positive COVID-19 test may resume study drug without an in-clinic visit, at the investigator's discretion, if COVID-19 symptoms are mild, and if the duration of interruption did not exceed 14 days.

Study drug may be resumed when the patient no longer presents an active infection (defined as resolution of symptoms or a negative SARS-CoV-2 test), as assessed by the Investigator and/or the patient's physician(s). If COVID-19 symptoms persist (e.g., loss of taste or smell), the patient should be encouraged to repeat SARS-CoV-2 testing in order to minimize the duration of study drug interruption.

For more information related to study drug management and COVID-19 see Appendix 1, Section 4.5.

## 10. STUDY DRUG MATERIALS AND MANAGEMENT

### 10.1. Study Drug

Bardoxolone methyl capsules, 5 mg (size #4), 10 mg (size #2), 15 mg (size #1), and 20 mg (size #0) may be used in this study. The 30 mg dose will be given as two 15 mg capsules. Placebo capsules will have matching capsule sizes to have the same appearance as the active doses.

### 10.2. Study Drug Packaging and Labeling

The study drug will be supplied as either individual bottles (5, 10, 20 mg dose) or in tamper-evident kits containing two high-density polyethylene (HDPE) bottles (30 mg dose as 2 x 15 mg capsules). Each bottle will utilize foil induction-seal liners and a child-resistant closure. Each bottle of study drug will contain 30 capsules of 5 mg, 10 mg, 15 mg, or 20 mg strength bardoxolone methyl or the matching placebo capsules. Each bottle will also contain desiccant insert(s) that must not be ingested. Labeling on each kit bottle will contain at minimum the following information:

- Medication ID number;
- Protocol 402-C-1808;
- Caution Statement: New Drug – Limited by Federal Law to Investigational Use. Keep out of reach of children;
- Control or lot number;
- Store at 15° – 25°C (59° – 77°F);
- Reata Pharmaceuticals, Inc., Irving, TX.

When applicable, a double-panel label will be presented on the treatment kit carton containing this and other information. Additionally, labeling, in the relevant local languages for study drug use and distribution in the EU shall adhere to current Eudralex, Volume 4 Annex 13 guidance and requirements.

In the event the investigational product is not packaged as intended or may not adhere to Current Good Manufacturing Practices (CGMP), a complaint should be filed with the Sponsor, ideally through the site's CRA. Guidance on filing study drug complaints is available in the Study Reference Manual, and attention should be given to ensure the patient number is not submitted within the complaint documentation.

### 10.3. Study Drug Storage

The stability of the drug product has been and is currently being evaluated in ongoing studies.

Investigative sites must store the investigational product in a secure location with room temperature conditions of 15° - 25°C (59° - 77°F).

If the investigational product is stored outside of the designated conditions, a temperature excursion notification should be submitted to the Sponsor for review and approval for use of the

affected study drug. Guidance on filing temperature excursions is available in the Study Reference Manual.

#### **10.4. Study Drug Administration**

Please refer to Section 9.10.13 for details on study drug administration. It is the responsibility of the investigator or designee to provide clear instructions to the patient regarding the number and type of capsules to be ingested at each study drug administration time point listed in Table 4. Patients must be instructed to continue taking study drug once daily through Week 100 unless: (1) the patient has been otherwise instructed by the investigator or (2) the patient has been formally discontinued from study treatment.

#### **10.5. Study Drug Accountability**

Study drug bottles and any unused capsules should be returned to the study staff for eventual disposition by the Sponsor. The investigator or designee will maintain a record of all study drug received, dispensed, and returned. The number of capsules returned at each visit will be recorded by the site for each bottle in the kit. The site will make these records available for Sponsor or designee review.

#### **10.6. Study Drug Handling and Disposal**

At any time during the conduct of the study, the Sponsor or its designee will direct the site regarding the final disposition of study drug. No study drug shall be destroyed by the clinical site unless agreed upon in writing by the Sponsor. Documentation of study drug disposition will be retained with the investigator. Refer to the IP Handling Manual for detailed instructions on study drug handling and disposal.

## **11. SAFETY ASSESSMENTS**

### **11.1. Safety Parameters**

To avoid inter-observer variability, every effort should be made to ensure that the same individual who made the initial baseline determinations completes all safety assessments. Safety parameters include vital sign measurements, ECG results, AEs, SAEs, weight, and laboratory test results.

### **11.2. Adverse and Serious Adverse Events**

#### **11.2.1. Definition of Adverse Events**

##### **11.2.1.1. Adverse Event**

An AE is defined as any untoward medical occurrence in a patient regardless of its causal relationship to study drug. An AE can be any unfavorable and unintended sign (including any clinically significant abnormal laboratory test result), symptom, or disease temporally associated with the use of the study drug, whether it is considered to be study-drug related. Included in this definition are any newly occurring events or previous conditions that have increased in severity or frequency since the administration of study drug.

All AEs that are observed or reported by the patient during the study (from administration of the first dose until the Week 112 (B) study visit as indicated in Table 4) must be reported, regardless of their relationship to study drug or their clinical significance.

For patients who discontinue study drug early (prior to Week 100) and continue to be followed in the study, all AEs should be recorded for 12 weeks following the patient's last dose of study drug. Beyond 12 weeks after the patient's last dose, only those AEs that are relevant to the clinical condition including kidney disease, may have an impact on kidney function, or may impact the interpretation of safety or efficacy data must be reported.

AEs that are related to study procedures should be reported independent of the patient's study drug status or duration since the patient's last dose of study drug. SAEs, if considered related to study drug, can be reported at any time during the study duration.

##### **11.2.1.2. Serious Adverse Event**

An SAE is any AE occurring at any dose and regardless of causality that:

- Results in death;
- Is life-threatening;
- Requires inpatient hospitalization or prolongation of existing hospitalization;
- Results in persistent or significant incapacity or substantial disruption of the ability to conduct normal life functions;
- Is a congenital anomaly or birth defect in an offspring of a patient taking study drug;
- Is an important medical event.

The term "life-threatening" refers to an event in which the patient was at immediate risk of death at the time of the event. It does not refer to an event that hypothetically might have caused death if it were more severe.

Important medical events are those that may not meet any of the criteria defined above; however, they may be considered serious when, based upon appropriate medical judgment, they may jeopardize the patient and may require medical or surgical intervention to prevent one of the other outcomes listed in the SAE definition.

Pregnancy is not considered an AE; however, information will be collected for any pregnancies that occur during the study (from the time of the first dose of study drug until the Week 112 (B) study visit indicated in Table 4, as appropriate). Certain pregnancy outcomes will require submission as an SAE (see Section 9.8).

The investigator is responsible for reporting to Reata or designee all AEs and SAEs that are observed or reported by the patient during the study (from the time of administration of the first dose of study drug until the Week 112 (B) study visit indicated in Table 4), including events resulting from protocol-associated procedures as defined in relevant legislation, and regardless of their relationship to study drug or their clinical significance. For patients who discontinue study drug early, SAEs should be reported through 12 weeks following the date of last dose of study drug. SAEs, if considered related to study drug, should be reported at any time during the study. The Sponsor may request additional information from the investigator to ensure the timely completion of accurate safety reports.

All SAEs reported or observed during the study must be followed to resolution or until the investigator deems the event to be chronic or the patient to be stable. Reata or designee may contact the investigator to obtain additional information on any SAE which has not resolved at the time the patient completes the study.

For information on ESKD related SAEs see section 9.1.9.

### **11.3. Eliciting Adverse Event Information**

At every study visit, patients must be asked a standard, non-directed question, such as, "How have you been feeling since your last visit?" to elicit any medically related changes in their well-being. They may also be asked if they have been hospitalized, had any accidents, used any new medications, or changed concomitant medication regimens (including prescription drugs, over-the-counter medications, vitamins, herbal products, and minerals). Responses must be documented in the source documents.

In addition to patient observations, AEs must be documented for any clinically significant diagnosis resulting from abnormal laboratory test values, physical examination findings, or ECG abnormalities, or from other documents that are relevant to patient safety.

### **11.4. Assessment of Causality**

The investigator must use the following classifications and criteria to characterize the relationship or association of the study drug in causing or contributing to the AE:

Not Related: This relationship suggests that there is no association between the study drug and the reported event.

Unlikely Related: This relationship suggests that the temporal sequence of the event with study drug administration makes a causal relationship improbable and/or other factors also provide plausible explanations.

Possibly Related: This relationship suggests that treatment with the study drug caused or contributed to the AE. That is, the event follows a reasonable temporal sequence from the time of study drug administration, and/or, follows a known response pattern to the study drug, but could have been produced by other factors.

Probably Related: This relationship suggests that a reasonable temporal sequence of the event with study drug administration exists and, based upon the known pharmacological action of the drug, known or previously reported adverse reactions to the drug or class of drugs, or judgment based on the investigator's clinical experience, the association of the event with study drug administration seems likely.

Definitely Related: This relationship suggests that a definite causal relationship exists between the drug administration and the AE, and other conditions (e.g., concurrent illness, progression/expression of disease state, or concurrent medication reaction) do not appear to explain the event.

For regulatory reporting purposes, an adverse event is considered to be related when the causality evaluation is either "Definitely Related, Probably Related, or Possibly Related." An adverse event is considered to be not related when the causality evaluation is either "Unlikely Related or Not Related."

## **11.5. Assessment of Severity**

The investigator will grade the severity of the AEs as mild, moderate, or severe using the following definitions:

Mild: Symptoms causing no or minimal interference with usual social and functional activities

Moderate: Symptoms causing greater than minimal interference with usual social and functional activities

Severe: Symptoms causing inability to perform usual social and functional activities

## **11.6. Recording Adverse Events**

All conditions present prior to the administration of the first dose of study drug (Day 1) should be documented as medical history. After the first dose, documentation of AEs shall continue until the Week 112 (B) study visit, as indicated in Table 4, regardless of their relationship to study drug or their clinical significance. For patients who discontinue study drug early (prior to Week 100) and continue to be followed in the study, all AEs should be recorded for 12 weeks following the patient's last dose of study drug. Beyond 12 weeks after the patient's last dose, only those AEs that are relevant to the clinical condition including kidney disease, may have an impact on kidney function, or may impact the interpretation of safety or efficacy data must be reported.

AEs that are related to study procedures should be reported independent of the patient's study drug status or duration since the patient's last dose of study drug.

Information to be collected includes type of event, date of onset, date of resolution, investigator-specified assessment of severity and relationship to study drug, seriousness, as well as any action taken.

For guidance on how to handle AEs that change in severity (e.g., worsening or improving), see the eCRF Completion Guidelines. All drug-related (possibly, probably, or definitely related, see Section 11.4) AEs and clinically significant abnormal laboratory test results reported or observed during the study must be followed to resolution (either return to baseline, within normal limits, or stabilization). All non-drug related AEs or clinically significant abnormal laboratory test results will be followed through the Week 112 (B) study visit or for 12 weeks following the last dose for patients who discontinue study drug early.

AEs resulting from concurrent illnesses, reactions to concurrent illnesses, reactions to concurrent medications, or progression of disease states must also be reported. Preexisting conditions (present before the start of the AE collection period) are considered concurrent medical conditions and should NOT be recorded as AEs. However, if the patient experiences a worsening or complication of such a concurrent condition, the worsening or complication should be recorded as an AE. Investigators should ensure that the AE term recorded captures the change in the condition (e.g., “worsening of...”). Any improvement in condition should be documented per Section 9.10.11.

Each AE should be recorded to represent a single diagnosis. Accompanying signs (including abnormal laboratory test values or ECG findings) or symptoms should NOT be recorded as additional AEs. If a diagnosis is unknown, sign(s) or symptom(s) should be recorded as an AE(s). Changes in laboratory test values or ECG parameters are only considered AEs if they are judged to be clinically significant (i.e., if some action or intervention is required or if the investigator judges the change to be beyond the range of normal physiological fluctuation). If abnormal laboratory test values or ECG findings are the result of pathology for which there is an overall diagnosis (e.g., increased creatinine levels in renal failure), only the diagnosis should be reported as an AE.

Elective procedures (surgeries or therapies) that were scheduled prior to the start of AE collection are not considered AEs. These elective procedures should not be recorded as AEs but should be documented in the patient’s source documents as elective (e.g., elective periodontal surgery). However, if a pre-planned procedure is performed early (e.g., as an emergency) because of a worsening of the preexisting condition, the worsening of the condition should be captured as an AE.

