9.1.2. Summaries of Adverse Events

Treatment-emergent adverse events and OTEAEs are summarized by treatment. For each treatment, SOC, and PT, the number and percentage of patients reporting an event is calculated. In summary tables, SOC is presented alphabetically and events within each SOC are presented by decreasing frequency count. Additionally, summary tables of events within PTs are presented by decreasing frequency count may be generated.

Summary tables (number and percentage of patients and events) of TEAEs (by SOC and PT) are provided by treatment as follows:

- All TEAEs
- All related TEAEs (definitely, probably, or possibly related)
- All TEAEs by severity
- All serious TEAEs (including deaths)
- All non-serious TEAEs
- All related serious TEAEs (including deaths)
- All TEAEs leading to permanent discontinuation of study drug
- All TEAEs leading to study drug interruption
- All TEAEs leading to dose de-escalation
- TEAEs by time to onset (≤ 12 weeks and > 12 weeks)
- TEAEs exhibited in $> 5\%$ of patients in either treatment group

Listings are provided showing:

- All AEs
- Deaths
- SAEs
- AEs leading to permanent discontinuation of study drug
- TEAEs leading to study drug interruption
- TEAEs leading to dose de-escalation

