The off-treatment periods between Week 48 to Week 52 prior to protocol version 6 and Week 100 to Week 104 will be analyzed by the summary of days since last dose. Indeed, for patients with a Week 52 off-treatment analysis visit, summary statistics of days since last dose are generated. Similarly, for patients with a Week 104 analysis visit, summary statistics of days since last dose are generated.

The number and percentage of patients are summarized by treatment group for Drug Interruption not related to COVID-19:

- Interruption Type (Primary Investigator (PI) initiated, Patient Reported)
- Primary reason for interruption (AE, Elevated Transaminase not clinically significant (NCS), Elevated BNP NCS, Fluid Overload NCS, Weight Gain NCS, Weight Loss NCS, Other)

Drug Interruption due to COVID-19 will also be summarized as specified in Section 11.1.

Patients not at per-protocol dose are listed, including reasons.

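### SAP 9.2 allows interruptions for transaminase or BNP elevations to be coded not clinically significant and separate from AE, although Protocol 11.6 makes a laboratory change that requires action an AE; the table of TEAEs leading to interruption may therefore be incomplete

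*Protocol*

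**What the plan says.** **When a laboratory finding is an AE.** Under Protocol 11.6 a laboratory or ECG change is an AE only if it is "judged to be clinically significant (i.e., if some action or intervention is required"; the explanation in full is "i.e., if some action or intervention is required or if the investigator judges the change to be beyond the range of normal physiological fluctuation". The same paragraph adds that, where an overall diagnosis explains the finding, "only the diagnosis should be reported as an AE".

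**General definition.** Protocol 11.2.1.1: "An AE can be any unfavorable and unintended sign (including any clinically significant abnormal laboratory test result), symptom, or disease". AEs are reported "regardless of their relationship to study drug or their clinical significance".

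**When drug is stopped.** Protocol 9.1.2, Table 5, requires a temporary stop for four listed ALT/AST criteria. Protocol 9.1.1 requires a stop when prompted by BNP elevation, sudden weight gain, or clinical signs and symptoms. Protocol 9.1.4 asks for a temporary stop in adolescents who lose more than 5% of Day 1 weight.

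**How interruptions are reported.** SAP 9.2 summarizes the primary reason for interruption by treatment group. The first category is AE; the others are "Elevated Transaminase not clinically significant (NCS), Elevated BNP NCS, Fluid Overload NCS, Weight Gain NCS, Weight Loss NCS, Other". Separately, SAP 9.1.2 lists among its by-treatment AE tables "All TEAEs leading to study drug interruption".

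**The concern.** The protocol's test for a laboratory AE turns on whether action is required. Stopping study drug is an action, and for transaminases and BNP the protocol itself requires it. A category that describes such an interruption as both not clinically significant and something other than an AE conflicts with that test.

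If a site selects an NCS reason and enters no AE, the patient does not appear among TEAEs leading to interruption, or in any other TEAE table for that finding. Protocol 5.1.2 links transaminase rises and fluid overload to the drug, so omissions would be expected more often in the active arm and would shrink the absolute difference between arms. Safety and tolerability is a primary objective (Protocol 6.1.1, SAP 3.1.1). With development discontinued (SAP Section 2) and all objectives carrying nominal significance levels only (SAP 8.3), the safety tables are a main product of the study.

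**Working it through.** The plan states no figure for interruptions, so there is nothing to reproduce. The check is a comparison of texts, category by category.

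1. **Elevated Transaminase NCS.** This is a laboratory value, so the 11.6 clause applies. Where a Table 5 stopping criterion is met, action is required and the change is an AE. The conflict is direct. It is less clear for a discretionary or patient-initiated hold below those criteria, where action was taken but may not have been required.
2. **Elevated BNP NCS.** This is also a laboratory value. As 9.1.1 is written, BNP elevation is one of the prompts for stopping drug, so the conflict is the same.
3. **Fluid Overload NCS.** This is not a laboratory or ECG value, so the 11.6 clause does not reach it. The question arises under 11.2.1.1, where an unfavorable sign, symptom or disease is an AE without a test of clinical significance. Confirmed fluid overload would fit that definition; a hold on suspicion, followed by an unremarkable assessment, need not.
4. **Weight Gain NCS and Weight Loss NCS.** These are not laboratory values either. A precautionary hold after a weight trigger need not be an AE.
5. **The diagnosis exception in 11.6.** It changes which term is recorded. An AE record still exists, so it does not explain an NCS category.

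**Does an NCS reason remove the patient from the TEAE table?** Only if no AE was entered, or if the table is built from the interruption reason. SAP 9.2 describes a primary reason for interruption. Protocol 11.6 has each AE record capture any action taken. Neither document says that one excludes the other, or which form feeds the SAP 9.1.2 table.

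**A ceiling for one component.** Every Table 5 stopping criterion needs ALT or AST above 3 × ULN. Protocol 5.1.2.2 gives 4% to 11% of patients above that level in earlier studies. Assuming the rate carries over and the planned arm is filled:

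- Arm size: 850 / 2 = 425
- Lower: 0.04 × 425 = 17
- Upper: 0.11 × 425 = 46.75, about 47

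So at most about 17 to 47 active-arm patients could have a Table 5 transaminase stop. The true number should be lower, because Table 5 does not require a stop for values above 3 × ULN alone. How many would be coded NCS without an AE record is not known.

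**Illustration of the effect (all inputs assumed).** Suppose 20% of active and 8% of placebo patients interrupt for these findings, and a share s in each arm is coded NCS with no AE record. The table then shows (1 − s) × 20% against (1 − s) × 8%:

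| s | Active | Placebo | Difference | Ratio |
|---|---|---|---|---|
| 0 | 20% | 8% | 12 points | 2.5 |
| 0.5 | 10% | 4% | 6 points | 2.5 |
| 1 | 0% | 0% | 0 points | not defined |

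The absolute difference shrinks in proportion to s. The ratio does not change while s is equal in both arms.

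**The case against.** The strongest reply has four parts.

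- **The information is already reported by arm.** SAP 9.2 shows AE and every NCS reason in one summary by treatment group. SAP 9.5.2 and 9.5.2.1 report ALT, AST and BNP shifts and thresholds whether or not an AE was entered, and SAP 9.7 reports weight. This stands: at most the TEAE tables are incomplete. But the threshold tables count values, not values that stopped drug; the transaminase thresholds are broken down by maximum dose received; and no visible output combines AE and NCS interruptions.
- **Undercounting is not shown.** A reader might infer that NCS-coded patients are necessarily absent from the TEAE table. The documents do not support that. An AE may have been recorded alongside the NCS reason, and the eCRF and its completion guidelines are not available to settle it.
- **The 11.6 clause does not cover all five categories.** A reader might take fluid and weight reasons as contradicting it too. They do not, for the reasons in the working. This also stands.
- **Recoding would be unsound.** A reader might conclude that the analyst should simply count NCS interruptions as TEAEs. Without an AE entry there is no term, severity or relatedness, so they cannot be placed in tables by system organ class and preferred term, and the step would override the investigator. This stands, and recoding is not proposed.

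Safety summaries are also descriptive and generally untested (SAP Section 9), so no decision rule depends on the table. That limits the consequence but does not remove the inconsistency.

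**Conclusion.** The conflict between SAP 9.2 and Protocol 11.6 is real for transaminase and BNP elevations that require drug to be stopped. Its effect is a risk of undercounting, of unknown size, in the table of TEAEs leading to interruption, and it materializes only where such an interruption has no AE record. It is likely greater in the active arm. That direction rests on the drug effects described in Protocol 5.1.2. It is firmer for transaminases, which rose in almost all treated patients, than for BNP, because the increased fluid-overload risk came from one trial in stage 4 CKD and this protocol excludes patients with the identified risk factors. The 17 to 47 figure is a conditional ceiling on mandated transaminase stops, not an estimate of omissions, and it assumes a full arm of 425.

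Fluid Overload NCS is a related question under 11.2.1.1, and weight-triggered holds need not be AEs. The documents do not support a claim that the drug's known harms go unreported. The point deserves action because the correction is cheap and concerns a primary objective.

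**What to change.** 1. Before database lock, list every interruption coded Elevated Transaminase NCS, Elevated BNP NCS or Fluid Overload NCS that has no matching AE record, and query each against Protocol 11.2.1.1 and 11.6. The investigator decides whether it is an AE; the analyst recodes nothing automatically.
2. Beside the SAP 9.1.2 table of TEAEs leading to interruption, add one by-arm row: any interruption for an AE or for a transaminase, BNP, fluid or weight finding.
3. Reconcile the NCS categories in SAP 9.2 with Protocol 11.6: state when NCS may be used, and which form feeds the SAP 9.1.2 table.

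No interruption criterion changes. The cost is SAP wording, one table row and some data queries; SAP 9.2 already plans to summarize these reasons, so no new data should be needed. The downside for the sponsor is that reported interruption counts would rise, mostly in the active arm.
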